### Model Results Presentation

- Least-square (LS) means and LS mean change from baseline values for each type of subject will be presented with their associated standard errors as well as 95% CIs. The estimated difference of interest (Overall COPD subjects, GOLD I-IV, chronic bronchitis, healthy control) defined in section 7.2 along with corresponding standard error, 95% CI for each visit will be presented.
- The LS mean differences (and associated 95% CIs) for all visits will be presented in tables.
- The LS mean change from baseline values (and 95% CIs) for all visits will be presented for each subgroup.

### Model Checking & Diagnostics

Refer to [Appendix 7: Model Checking and Diagnostics for Statistical Analyses](#).

### Subgroup Analyses

- Subgroup analysis will be performed as specified in section 5.3.2. This will include analysis by age (<65 years, ≥65), gender (Female, Male), GOLD I-IV baseline reversibility, number of exacerbations in previous year (2, 3, ≥4) and smoking status (ever/never smoker).
- Statistical analyses for sub-cohort participants should be conducted for scheduled visits and exacerbation visits, respectively.

### Sensitivity and Supportive Analyses

- A sensitivity analysis will also be performed on the subjects in completer Population.
- Multiple imputation will be utilized under the assumption of MAR for MMRM model for participants who withdrawal from the study as well as lost to follow up the study,

post- withdrawal counts were imputed conditional upon the subject's own observed measurements prior to withdrawal.

Endpoint / Variables

 
Rate of moderate/severe exacerbations
 
 
Moderate and severe exacerbations occurring from baseline will be included in the analysis.
 
For all summaries and analyses, exacerbations occurring within 7 days from the end of the first exacerbation of each other within a given subject will be handled as a continuation of the same exacerbation, assigned to the greatest severity. All individual exacerbations will be listed.

Model Specification

 
Generalized linear model assuming a negative binomial distribution
 
Terms in the model: 
 
Response: number of moderate/severe exacerbations experienced per subject.
 
Categorical: visit, type of subjects (i.e. GOLD I-IV, chronic bronchitis, healthy control), gender, smoking status, exacerbation history (moderate/severe), site (type of hospital), maintenance therapy (Y/N) and ICS containing (Y/N), Childhood chest disease (Y/N) and biomass fuel exposure (Y/N).
 
Continuous: age, baseline FEV1, time on study
 
Offset: logarithm of time on study
 
 
 

Model Results Presentation

 
The model estimated mean rate of exacerbations per year will be calculated using the observed marginal distributions of the study population covariates by inclusion of the OM (obsmargins) option in the LSMEANS statement of the GENMOD procedure. The estimated mean rate of moderate/severe exacerbations per year for each type of subjects (Overall COPD subjects, GOLD I-IV, chronic bronchitis, healthy control) and the rate ratio for each type of subjects with 95% confidence intervals and associated p-values will be presented in a table and associated figure.
 

Endpoint(s)

 
Change from baseline in CAT score
 

Model Specification

 
Mixed Models Repeated Measures (MMRM) model.
 
While missing data are not explicitly imputed in the MMRM analyses, there is an underlying assumption that the data are missing at random.
 
The MMRM analysis for CAT score measurements at on-site visit (month 6, months 18 and month 30) and trimonthly telephone interview (month 3, month 9, month 12, month 15, month 21, month 24, month 27). Additional visits will be added for sub-cohort (month
 

2, month 4, month 5, month 19, month 20, month 22 and month 23). The MMRM analysis for CAT score will include CAT scores at each visit.
 
 
• Terms in the model: 
 
• Response: Change from baseline in CAT score at each visit.
 
• Categorical: visit, type of subjects (i.e. GOLD I-IV, chronic bronchitis, healthy control), gender, smoking status, site (type of hospital), maintenance therapy (Y/N) and ICS containing (Y/N).
 
• Continuous: age, baseline FEV1, baseline CAT score, count of COPD exacerbations,
 
• Interaction: baseline CAT score*visit, type of subjects*visit
 
• Repeated: visit
 
 
 
• The model will be fitted with an unstructured variance-covariance matrix.
 
• The Kenward and Roger method (KR) for approximating the denominator degrees of freedom and correcting for bias in the estimated variance-covariance of the fixed effects will be used.
 
• Baseline is defined in Section 5.2.
 
• Two models will be fitted; one with a response variable of change from baseline and one with the response variable as the raw value.
 

Model Results Presentation

 
• Least-square (LS) means and LS mean change from baseline values for each type of subject (Overall COPD subjects, GOLD I-IV, chronic bronchitis, healthy control) will be presented with their associated standard errors as well as 95% CIs. The estimated difference along with corresponding standard error, 95% CI for each visit will be presented.
 
• The LS mean differences (and associated 95% CIs) for all visits will also be presented in tables.
 

Model Checking & Diagnostics

 
• Refer to Appendix 7: Model Checking and Diagnostics for Statistical Analyses.
 

Subgroup Analyses

Subgroup analysis will be performed as specified in section 5.3.2. This will include analysis by age (<65 years, <math>\geq 65</math>), gender (Female, Male), GOLD I-IV baseline reversibility, number of exacerbations in previous year (2, 3, <math>\geq 4</math>), maintenance treatment (Y/N) and ICS containing (Y/N) and smoking status (ever/never smoker).
 
For CAT score, analyses will be conducted for main cohort and sub-cohort, respectively. Statistical analyses for sub-cohort participants should be conducted for scheduled visits and exacerbation visits, respectively.

Sensitivity and Supportive Analyses

 
• A mixed effects model whereas time is entered as a random effect will be analysed as a supportive analysis to estimate the longitudinal changes if necessary.
 

Endpoint / Variables

 
• Rate of decline in CAT score
 

Model Specification

 
Random coefficients model (a particular form of a mixed effects model)
 
For the analyses of rate of decline, each subject's actual time on study will be used, rather than assigning visit as a categorical variable.
 
While missing data are not explicitly imputed in the mixed effects model, there is an underlying assumption that the data are missing at random. Participants and time on study will be random effects.
 
Terms in the model: 
 
Response: CAT score at each visit.
 
Categorical: type of subjects (i.e. GOLD I-IV, chronic bronchitis, healthy control), smoking status, site (type of hospital).
 
Continuous: age, baseline CAT score, count of COPD exacerbations, time on study
 
Interaction: type of subjects*time on study
 
 
 
The model will be fitted with an unstructured variance-covariance matrix. If the model fails to converge, then alternative covariance structures may be investigated.
 
Only CAT score measured after baseline are used as the response. So in this model a subject needs to have at least one post-baseline value to be included in the analysis.
 
To investigate the effects of a particular covariates 
 
Base model: type of patients, time on study, type of patients* time on study (interaction term) terms for the covariate and covariate-by-time interaction were added to the base model described above, these covariates including gender, smoking status, age, count of COPD exacerbations, maintenance therapy and ICS containing treatment
 
The slopes were estimated for each type of subjects ((i.e. GOLD I-IV, chronic bronchitis, healthy control)
 
 
 

Model Results Presentation

 
The estimate of the slope is the parameter estimate associated with the type of subjects (Overall COPD subjects, GOLD I-IV, chronic bronchitis, healthy control) by time interaction in the model. The adjusted means, pairwise differences in different type of subjects, p-values and 95% confidence limits for the differences of interests will be summarized overall and also estimated for each visit.
 

Model Checking & Diagnostics
Refer to Appendix 7: Model Checking and Diagnostics for Statistical Analyses .

Endpoint(s)
Test the sensitivity and specificity of CAPTURE to identify possible COPD patients in a Chinese population
Model Specification

 
CAPTURE (COPD Assessment in Primary Care to Identify Undiagnosed Respiratory Disease and Exacerbation Risk) is a simple, five-item, patient-completed questionnaire.
 
The algorithm is a simple summation of patient responses to each of the five items. (For Question1-4, Score 0 for No, Score 1 for Yes, Question 5, Score 0,1,2. So the total score is
 

ranging from 0 to 6). Higher score means higher risk of COPD (0-1 is at low risk, 2-6 is at high risk).

- Cut-off value (2 or 3 points) are used to test the sensitivity and specificity of CAPTURE questionnaire.
- Reference standard: COPD patients (GOLDI and GOLDII) and non-COPD patients (Chronic Bronchitis and never smoker healthy control)

Cut Point:	COPD patients	Non-COPD patients
Capture score ( $\geq$ Cut-off)	TP	FP
Capture score ( $<$ Cut-off)	FN	TN

TP = number of true positive events

FP = number of false positive events

TN = number of true negative events

FN = number of false negative events

Positive predictive value (PPV)=TP/(TP+FP)

Negative predictive value (NPV)=TN/(TN+FN)

Estimated sensitivity = 100% \* TP/(TP+FN)

Estimated specificity = 100% \* TN/(FP+TN)

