### 3. BACKGROUND AND STUDY RATIONALE

COPD is a leading cause of morbidity and mortality resulting in significant humanistic and economic burden to patients, healthcare system and society worldwide. COPD prevalence in China has been significantly increasing. A national screening survey, conducted in 2002-2004, reported that the overall prevalence of spirometry-defined COPD among people over 40-year-old was 8.2% in China [Zhong, 2007]. The recently published China Pulmonary Health study (2018) indicated the prevalence of COPD among Chinese over 40 years old had increased to 13.7% [Wang, 2018]. A study in 2013 including 634 COPD patients from 83 tertiary hospitals in 17 provinces in China estimated the average cost of COPD per patient per year to be RMB 20,107.58. Further, COPD led to a large productivity loss of RMB 6,941.33 yuan/per person-year; the value of working time loss was RMB 613.86 yuan/per person-year [Li, 2015]. Although COPD management in China has been greatly improved over the past decades, many challenges persist. One of them is substantial under-diagnosis: up to 65% of people with airflow limitation pattern compatible with COPD were found not to have a clinical COPD diagnosis [Zhong, 2007]. Further, majority of COPD patients (64.7%) exhibit high symptom burden, defined as at least one respiratory symptom (cough, phlegm, wheezing, and breathlessness), despite treatment [Zhong, 2007].

COPD prevalence and disease burden have been well studied in North America and Western Europe through large cohort studies. The ECLIPSE study recruited patients with moderate-severe airflow limitation from secondary care [Vestbo, 2008; Vestbo, 2014; Faner, 2014]; COPDGene [Regan, 2010], COPDMAP [Wang, 2017] and SPIROMICS [Couper, 2014] largely recruited patients of a wide range of disease severity from a variety of healthcare settings. However, so far there have been no dedicated cohort studies conducted in China with a specific focus on high density phenotyping of COPD, including biomarkers and clinical features associated with disease activity, severity and progression in China. Existing large populational cohorts, like the China Kadoorie Biobank, inform on the extent of disease burden of airflow limitation; however, due to its general population-based nature, they provide only limited information on clinical and humanistic burden and therapeutic management of diagnosed COPD [Kurmi, 2014].

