## 4. OBJECTIVES AND ENDPOINTS

| Research Questions & Objectives   | Endpoints   |
|---|---|
| 
Evaluate whether the predictors of COPD disease progression identified in Western cohorts are applicable in China.
 
 
To evaluate disease progression in COPD and non-COPD participants over 2.5 years as assessed by lung function, exacerbation frequency, health status, lung HRCT scan, and changes in physical activity.
 
 | 
Main cohort
 
Change from baseline in forced expiratory volume in 1 second (FEV1) and rate of decline in FEV1
 
Change from baseline forced vital capacity (FVC) and rate of decline in FVC
 
Rate of moderate/severe exacerbations*
 
Change from baseline in COPD Assessment Test (CAT) score
 
Assess CAPTURE to identify under diagnosed COPD patients in Chinese population
 
Frequency of Clinically Important Deterioration (CID) and its components
 
Death
 
Additional for sub-cohort
 
Change in Evaluating Respiratory Symptoms in COPD (E-RS: COPD) scores
 
Characterization of EXAcerbation of COPD Tool (EXACT) events
 
Change from baseline in airway thickness by lung HRCT
 
Change in lung density by lung HRCT
 
Change in physical activity measures (e.g. Daily steps, bouts of activity per day)
 |
| 
Characterise stable disease and exacerbation phenotypes in China through assessment of blood biomarkers, lung microbiome and radiological features of COPD
   | 
Main cohort:
 
Plasma fibrinogen, Serum high-sensitivity C-Reactive Protein (hsCRP)
 
Differential blood cell count (including eosinophils, neutrophils) and hemoglobin
 
Additional for sub-cohort
 
Blood biomarkers including but not limited to Serum interferon- <math>\gamma</math> -inducible protein -10 (IP-10), soluble Receptor for
   |

| Research Questions & Objectives  | Endpoints   |
|--|---|
|  | 
Advanced Glycation End Products (sRAGE), Club cell protein (CC16)) and HbA1c
 
Sputum microbiome as assessed by molecular methods
 
Sputum total differential cell counts and percentage
 
CCI
  |

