### **9.2. Other PROs and Questionaries**

Summary of SGRQ Total and subscales will be provided by arm.

Summary of mMRC Dyspnea score will be provided by arm.

Summary of CAPTURE score at baseline and V3 will be provided by arm. CAPTURE score category (defined as  $\geq 2$  and  $< 2$ ) will also be provided in the same table.

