## 5. CONSIDERATIONS FOR DATA ANALYSES AND DATA HANDLING CONVENTIONS

### 5.1. Number of Participants and sub-groups

A total of 2,000 participants are planned to be enrolled, consisting of 1,700 participants with COPD, 180 with chronic bronchitis but without fixed airflow limitation, and 120 never smoker healthy control. Specifically, COPD subjects will be classified using the GOLD grades I – IV (i.e. mild, moderate, severe and very severe). To better understand the disease progression of early stage COPD, i.e. GOLD I and II grades, COPD participants will be recruited in the following manner: GOLD I: 700, GOLD II: 700, GOLD III: 200, GOLD IV: 100 ([Figure 1](#)[Error! Reference source not found.](#)).

[figure not shown]
Figure 1 Study Population Schematic

More assessments will be conducted among the 400 Biomarker & Digital sub-cohort participants who will be all recruited from selected Type A hospitals. The sub-cohort consists of 50 never smoker healthy control, 100 chronic bronchitis (N never smoker: 25), 100 GOLD I (N never smoker: 25), 100 GOLD II (N never smoker: 25) and 50 GOLD III participants (N never smoker: 20) ([Figure 2](#)[Sub-cohort Population Schematic](#)). In GOLD I-III grades, certain number of COPD participants with previous exacerbation history (i.e. exacerbators) will be recruited (target number of subjects are as follows - GOLD I: 60 exacerbators, GOLD II: 60 exacerbators, GOLD III: 30 exacerbators). Further, a proportion of those who are maintenance inhaler treatment naïve will be recruited, aiming for: 10 participants who are maintenance inhaler treatment naïve

will be recruited among exacerbators and non-exacerbators in each GOLD I, II, III groups respectively (Figure 2). All patient population sizes are approximate and allow +/- 10% for feasibility.

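### SAP amendment 3 drops the protocol's CAPTURE accuracy endpoint without declaring it, and the superseded RAP analysis should not be put back unchanged

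*SAP*

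**What the plan says.** **Protocol.** The endpoint list in section 4 includes "Assess CAPTURE to identify under diagnosed COPD patients in Chinese population", and the synopsis lists the same item. The outcome rationale in section 5.4 says the purpose is to assess the questionnaire's sensitivity and specificity for case finding. CAPTURE is completed at baseline and Visit 3.

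**SAP amendment 3 (the current plan).** The endpoint table in 2.2 has no CAPTURE entry. Section 9.2 states: "Summary of CAPTURE score at baseline and V3 will be provided by arm". It adds a score category of ≥2 against <2 in the same table. Section 2.1, which lists departures from protocol amendment 02, covers populations, the ±90-day window, the rate of change in CAT and phenotype analyses. It does not mention CAPTURE. The version history describes amendment 3 only as a move to the SAP template with endpoints recategorised.

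**RAP amendment 2 (bound in the same file).** Section 7.4.1 has a 2×2 accuracy analysis. Its reference standard is "COPD patients (GOLDI and GOLDII) and non-COPD patients (Chronic Bronchitis and never smoker healthy control". It gives "Positive predictive value (PPV)=TP/(TP+FP" and the matching NPV formula, both from raw counts. Its results presentation names only sensitivity and specificity. RAP 2.1 does declare that the endpoint was reworded, from underdiagnosed COPD to possible COPD.

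**The concern.** A protocol endpoint has lost its planned analysis, and the section meant to record such changes is silent. A reader of the study report would see CAPTURE scores by arm, with no stated accuracy estimate and no explanation.

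The by-arm table also does not match the question. COPD entry (protocol 6.1) rests on spirometry and does not restrict prior diagnosis, so each GOLD arm can mix patients already diagnosed and treated with those found at screening. Case finding concerns the second group.

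The obvious repair is to copy the RAP analysis back, and that would bring in two further problems. Its predictive values depend on a case share fixed by recruitment targets. Its specificity averages two groups selected at opposite ends of the symptom range: participants with chronic cough and phlegm, and never smokers with a CAT score below 10 and no significant disease.

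**Working it through.** **1. Where the endpoint goes.**

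| Place | CAPTURE content |
|---|---|
| Protocol 4 and 5.4 | Endpoint; sensitivity and specificity for case finding |
| RAP amendment 2, sections 2.1, 2.2 and 7.4.1 | Reworded endpoint, declared; 2×2 analysis |
| SAP amendment 3, section 2.1 | Not mentioned |
| SAP amendment 3, section 2.2 | Absent from endpoint table |
| SAP amendment 3, section 9.2 | Score and ≥2/<2 category by arm |

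**2. Quota counts.** COPD: "GOLD I: 700, GOLD II: 700, GOLD III: 200, GOLD IV: 100". Non-COPD: "180 with chronic bronchitis but without fixed airflow limitation, and 120 never smoker healthy control". The RAP comparison uses GOLD I and II only, so there are 700 + 700 = 1,400 cases and 180 + 120 = 300 non-cases.

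The documents state no CAPTURE accuracy figure to reproduce. The 700 per grade comes from the FEV1 precision calculation (protocol 10.1.3), which does reproduce:
- σp = √(3.8² + 12×3×233²/(2.5²×4×5)) = 125.1
- Completers = 1.96² × 125.1² × 2/15² = 534, against 525 stated (1.8% apart)
- 525/0.75 = 700

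So the case share was set by lung-function precision, not by the prevalence of COPD.

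**3. Case share.** 1400/1700 = 0.824. If the quotas move by 10% in opposite directions, the share runs from 1260/(1260+330) = 0.792 to 1540/(1540+270) = 0.851. Protocol section 3 reports that "the prevalence of COPD among Chinese over 40 years old had increased to 13.7"%.

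**4. Predictive values.** With prevalence p:
- PPV = Se·p / [Se·p + (1−Sp)(1−p)]
- NPV = Sp(1−p) / [Sp(1−p) + (1−Se)p]

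Take Se = Sp = 0.7 (assumed).
- Quota sample: TP = 980, FN = 420, FP = 90, TN = 210. PPV = 980/1070 = 0.916; NPV = 210/630 = 0.333.
- At p = 0.137: PPV = 0.0959/(0.0959 + 0.2589) = 0.270; NPV = 0.6041/(0.6041 + 0.0411) = 0.936.

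Over an assumed grid of Se and Sp from 0.5 to 0.9:

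| | Quota sample | At 13.7% |
|---|---|---|
| PPV | 0.82–0.98 | 0.14–0.59 |
| NPV | 0.18–0.66 | 0.86–0.98 |

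Neither pair of ranges overlaps.

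**5. Pooled specificity.** The weights are 180/300 = 0.6 for chronic bronchitis and 120/300 = 0.4 for healthy controls. If specificity were 0.40 and 0.90 respectively (assumed), the pooled value would be 0.6×0.40 + 0.4×0.90 = 0.60, which describes neither group.

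**The case against.** The strongest reply is that the current plan computes no PPV or NPV. The version history places SAP amendment 3 after RAP amendment 2. SAP 9.2 has no 2×2 table, and SAP Table 1 no longer lists the CAPTURE examination that RAP Table 1 put at the Visit 2 analysis. Even the RAP listed only sensitivity and specificity for presentation. All of this stands. A reader might infer from the RAP formulas that inflated predictive values will be published; the documents do not support that. The quota problem is a reason not to restore the RAP text, not an error in the current SAP.

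Second, RAP 2.1 openly changed the target from underdiagnosed to possible COPD, so counting known cases was a declared choice. That holds for the RAP. SAP 2.1 states its own departures from the same protocol amendment and does not carry this one over, and the protocol wording is unchanged.

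Third, a reader might conclude that no usable accuracy estimate remains anywhere. That goes too far. The share scoring ≥2 in a GOLD arm is sensitivity at that cut-off, and the share scoring <2 in the chronic bronchitis or control arm is specificity. RAP sensitivity in GOLD I–II also does not depend on the case-to-control ratio. What is missing is the stated estimates, the other cut-offs and the undiagnosed subgroup.

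**Conclusion.** The point holds as an undeclared loss of a protocol endpoint, together with a by-arm summary that cannot isolate previously undiagnosed COPD. These findings come from the documents and need no assumed figure.

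The caution about the RAP analysis rests on the 82% quota share, which is arithmetic, and on illustrative accuracy values, which are assumed. The direction is firm: for case finding, raw-count PPV is too high and NPV too low across the whole grid. The size is not firm:
- A fall in PPV from 0.92 to about 0.28 needs a positive likelihood ratio near 2.5, which the documents do not give.
- It is tempting to say NPV is understated by the same amount as PPV is overstated, but this is not general. With quota PPV held at 0.92, the PPV gap is 0.64, while the NPV gap is 0.66 at sensitivity 0.5, 0.40 at 0.9 and 0.26 at 0.95.
- The 13.7% covers all grades, diagnosed or not, so it only approximates the prevalence in a case-finding setting. Sensitivity and specificity from these selected groups may not transfer either.

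**What to change.** 1. **SAP 9.2:** add sensitivity and specificity of CAPTURE with 95% CIs at the cut-offs already named (≥2 in the SAP; 2 or 3 in the RAP, with supportive splits at 3 and 4), and say which is the main one.
2. **Specificity:** report it separately for chronic bronchitis and healthy controls.
3. **Sensitivity:** report it also in COPD participants with no COPD diagnosis or treatment before entry. Protocol 9.1 collects disease duration and treatment history at baseline; the SAP should state how these define the subgroup.
4. **PPV and NPV:** do not report them from the raw 2×2 counts. If they are wanted, derive them by Bayes' rule over a stated prevalence range, label them as such, and name the specificity used.
5. **SAP 2.1 and 2.2:** declare the change to the endpoint and its reason, or restore it to the endpoint table. If the accuracy analysis is dropped on purpose, say so in 2.1.

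The cost is SAP wording, one extra table and some precision. At an assumed specificity of 0.7, the 95% half-width 1.96×√(0.7×0.3/n) is 0.05 for n = 300 pooled, 0.07 for n = 180 and 0.08 for n = 120. The undiagnosed subgroup will be smaller than the full GOLD I–II group; the documents do not give its size.
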